#### Self-Reported Effects

The main self-reported effects outcome was the change in self-reported "craving a cigarette/nicotine" on the MNWS from before the 10-puff directed use bout to after at the final clinical laboratory session (Fri, week 2; session 4, study day 12). The change in "craving a cigarette/nicotine" was calculated for each participant by subtracting the pre-puff measurement from the post-puff measurement (i.e., cigarette craving suppression). Mann-Whitney U tests compared differences in cigarette craving suppression across the IQOS-M and IQOS-T groups (Stata 17).

Differences across experimental groups in pre- to post-puff changes in QSU-B Factor 1, pre- to post-puff changes in QSU-B Factor 2, pre- to post-puff changes in all MNWS items, PEQ subscales, and the study specific questions were explored at session 2 (OB; Fri, week 1), session 3 (IQOS; Mon, week 2), and session 4 (IQOS; Fri, week 2) using Mann-Whitney U tests. Exploratory analyses compared within-group differences in all self-reported effects outcomes at session 3 (IQOS; Mon, week 2; study day 8) to session 4 (IQOS; Fri, week 2; study day 12) using Wilcoxon Signed Rank tests. Wilcoxon Signed Rank tests compared self-reported effects outcomes associated with use of OB menthol cigarettes (Fri, week 1; study day 5) to IQOS (Friday, week 2; study day 12) within each experimental group. Differences in the pre-puff and post-puff values for items on the QSU-B and MNWS were explored within-group using Wilcoxon Signed Rank tests.

#### Experimental Tobacco Marketplace

The main ETM outcome was IQOS' CPE with respect to OB menthol cigarettes. Demand for all products in the ETM was converted to milligrams (mg) of nicotine to allow for cross-product comparisons (Bickel et al., 2018; Appendix 4) then log transformed (zero consumption values were converted to a nonzero integer by adding 0.1). CPE estimates for each alternative product in the ETM were estimated using an approach based on linear regression (Heckman, Cummings et al., 2017; Quisenberry, Koffarnus et al., 2016).

linear regression of log-transformed fixed-price alternative demand as a function of logtransformed OB menthol cigarette prices,

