Aim 2. Measure tobacco use patterns across IQOS flavor availability conditions to assess clinical lab result validity. During 7-day naturalistic evaluation outside of the clinical lab, participants will respond to daily Ecological Momentary Assessment (EMA) prompts by reporting OB and IQOS use.  $H_{2A}$ : Those in the IQOS-menthol condition will have a larger percentage reduction in average daily cigarettes consumed per day (Tues-Thurs) from the baseline to the intervention week, than those in the IQOS-tobacco condition.  $H_{2B}$ : IQOS use/day higher during the intervention week (Tues-Thurs) will be higher in the IQOS-menthol condition compared to the IQOS-tobacco condition.  $H_{2C}$ : Those with access to IQOS-menthol will replace a greater percentage of their total tobacco product consumption (cigarettes + IQOS) with IQOS products during the intervention week (Tues-Thurs) than will those with access to IQOS-tobacco.

Hypothesis  $H_{1A}$ ,  $H_{1D}$ , and  $H_{2A}$  constitute primary outcomes. All other hypothesis represent secondary outcomes.

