Aim 1: During the course of the clinical lab study set forth in Aim 1, participants will complete directed puffing bouts (10-puffs, 30 second interpuff interval) with either OB (baseline week) or their randomly-assigned IQOS product (intervention week). The interpuff interval is defined as the time between the start of 1 puff and the beginning of the next (Hiler et al., 2017). This procedure requires physiological monitoring of heart rate and blood pressure (sessions will be stopped if blood pressure ever exceeds 180/120) and venipuncture and/or catheter placement will be completed by [name], RN. One blood sample (7 mLs) will taken immediately before and immediately after a standard, controlled 10-puff directed puffing bout (total of 14 mL per session). A total of 56 mL of blood will be sampled for the entire study; this amount of blood sampling will occur at 4 sessions over a 12 day period and is less than a standard blood donation that is provided in a single sitting (473 mL). Outcome measures include changes in plasma nicotine and menthol concentration from pre- to post- puffing bout and subjective effects, including cigarette craving suppression as well as the direct effects of OB and IQOS. Following this procedure, participants will then complete an Experimental Tobacco Marketplace (ETM). In the ETM, participants will be asked to make purchasing decisions across an array of tobacco/nicotine products, including IQOS and OB, as their OB become increasingly expensive (prices will be presented in random order at each session [i.e., the order of pricetrials will be randomly determined for each session, but within a session each participant will face the same order of price-trials]). The minimum task time for the ETM will be set to 20 minutes (i.e., if a participant finishes all questions in the ETM before 20 minutes, they'll cannot progress to the next portion of the session until 20 minutes has elapsed). The primary outcome of interest is the cross-price elasticity of demand for IQOS as a function of OB price. Each session will begin by obtaining an exhaled Carbon Monoxide breath sample, as will be done in the in-person screening session, and asking participants whether they've abstained from using tobacco or nicotine products in the last 8 hours. Moreover, on the 2 Friday sessions, participants will complete a short "timeline follow back" assessment to report on their usage of cigarettes, IQOS, and other tobacco products during the preceding 3-days (Tues-Thurs). A timeline of session structure is provided below.

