### $log(Demand) = \beta_0 + \beta_1 log(OB Menthol Cigarette Price) + e,$

where  $\beta_0$  represented the cross-price intensity of demand,  $\beta_1$  represented the CPE of the fixedprice alternative as a function of OB menthol cigarette price (main outcome), and *e* was the error term. Mann-Whitney U tests compared the individual-level CPE estimates for IQOS across participants with access to both flavors of HeatSticks (IQOS-M group) to participants with access to only Regular/Tobacco HeatSticks (IQOS-T group) at the final clinical laboratory session (IQOS; Fri, week 2; session 4, study day 12). As an alternative strategy for calculating CPE estimates, demand for each fixed-price alternative was averaged within-group at each price trial in the ETM then a single regression for each group was fit to Equation 1. The resulting  $\beta_1$ coefficient estimates were compared across experimental groups using a linear combination of parameters approach.

To ensure data quality and that participants were responding to the price cues within the task, demand for OB menthol cigarettes in the ETM was modeled using an exponentiated demand equation (GraphPad Prism 9; Hursh & Silberberg, 2008),

$$Q = Q_0 + 10 * k (e^{(-\alpha(C * Q_0))}) - 1),$$

where *C* represented the cost of the OB menthol cigarettes, *Q* represented cigarette consumption at price *C*, *Q*0 represented OB menthol cigarette demand intensity (i.e., cigarette consumption at the lowest price trial), *k* represented the range of cigarette demand across price trials in log units, and  $\alpha$  was the free parameter that represented the rate of change in demand elasticity. *k* was set equal to 4.89 for all participants (Hursh & Roma, 2013; Hursh & Silberberg, 2008; Quisenberry, Koffarnus et al., 2016). Group-level averages for  $\alpha$  and R^2 were the outcomes of interest;  $\alpha$  was expressed in terms of log( $\alpha$ ) because  $\alpha$  values tend to be very small. OB menthol cigarette demand was also assessed for each participant using criteria (i.e., trend, bounce, reversal from zero) for identifying nonsystematic demand in purchase tasks (Stein, Koffarnus et al., 2015).

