Exploratory analyses compared the observed *cross-price intensity* of IQOS (i.e., demand for IQOS at the lowest price of OB menthol cigarettes [\$0.12/cigarette]) across the IQOS-M and IQOS-T groups using Mann-Whitney U tests. CPE estimates for all other alternative products were compared across experimental groups using Mann-Whitney U tests (individual-level analyses) and a linear combination of parameters (group-level analyses). Wilcoxon Signed Rank tests compared ETM outcomes (within-group) across sessions 2 (OB, Fri) and 4 (IQOS, Fri) as well as across sessions 3 (IQOS, Mon) and 4 (IQOS, Fri) to gauge if exposure to IQOS in the clinical laboratory or at home influenced purchasing decisions in the ETM.

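### H1D's individual slopes depend on the 0.1 given to zero IQOS demand; no planned analysis varies it, and the group-level check needs a participant-based standard error

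*Combined protocol and SAP*

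**What the plan says.** Section 1 names H1A, H1D and H2A and says they "constitute primary outcomes. All other hypothesis represent secondary outcomes". Section 6 repeats for the marketplace task (ETM) that "The primary outcome of interest is the cross-price elasticity of demand for IQOS as a function of OB price".

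The analysis is under Aim 1 Analyses, Experimental Tobacco Marketplace. "Demand for all products in the ETM was converted to milligrams (mg) of nicotine" and then logged, and "zero consumption values were converted to a nonzero integer by adding 0.1". Log demand is regressed on log own-brand price for each participant, and the slope is the cross-price elasticity (CPE). "Mann-Whitney U tests compared the individual-level CPE estimates for IQOS across participants with access to both flavors of HeatSticks" with those who could buy only the tobacco flavor, at session 4.

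As an alternative, demand for each product "was averaged within-group at each price trial in the ETM then a single regression for each group was fit to Equation 1", and the "coefficient estimates were compared across experimental groups using a linear combination of parameters approach". An exploratory analysis compares between arms, also by Mann-Whitney, "demand for IQOS at the lowest price of OB menthol cigarettes", which is $0.12 per cigarette.

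The only analyses labelled as sensitivity analyses are in Aim 2 and concern cigarette counts. The checks for nonsystematic demand apply to own-brand cigarettes, not to IQOS zeros.

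**The concern.** The logarithm of zero does not exist, so some value must stand in for it, and the slope then depends on that value. If IQOS is not bought when cigarettes are cheap, the stand-in sits at the low end of the price axis, where it has most leverage.

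What counts is the ratio of 0.1 to the mg credited to one stick. A small ratio makes a zero look like a steep drop, and a large ratio makes it look like a shallow one. The arms may differ in how often IQOS is not bought, because only IQOS-M participants can choose either flavor. The arms could then appear to differ in CPE when they do not, or a real difference could be hidden.

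The plan holds a natural check in its group-level regression. That check helps only if its uncertainty reflects variation between participants.

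**Working it through.** **Inputs from the documents.** 25 per arm (Section 3); lowest price $0.12; 0.1 for zeros; log-log slope; Mann-Whitney test. The plan gives no figure for the effect of zeros, so there is none to reproduce.

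**Assumed, because the supplied text does not give them.** Six prices doubling from $0.12; whole-stick purchases; the same mg per stick, m, for both flavors, with m = 1, 0.5 or 0.25; log-normal demand level (SD 0.8), lower in IQOS-T where zeros are unbalanced; elasticity SD 0.2; constant c = 0.1 in mg, for zeros only; two-sided 0.05; 1,000 runs per cell.

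**Step 1: dependence of one slope.** With x the centred log price, the slope is Σ x·ln(demand) / Sxx. For a participant whose only zero is at the lowest price, this equals A + (|x1|/Sxx) × ln(m/c), where A depends only on the sticks bought.

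- Six prices: |x1| = 2.5 ln 2 = 1.733; Sxx = 17.5 (ln 2)² = 8.408; ratio 0.206. A tenfold change in c moves the CPE by 2.303 × 0.206 = 0.47.
- Five prices: 2.303 × 1.386/4.805 = 0.66.
- Eight prices: 2.303 × 2.426/20.18 = 0.28.

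If only zeros are replaced, a participant with no zeros is unaffected, and one with all zeros has slope 0 for any c.

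**Step 2: two buyers, six prices, c = 0.1.** Purchases of 0, 1, 2, 3, 6, 10 sticks give CPE 1.19, 1.04 and 0.90 at 1, 0.5 and 0.25 mg per stick. Purchases of 1, 2, 3, 6, 10, 17 give 0.81 at every value. The gap shrinks from 0.38 to 0.09, but the order holds throughout. It would reverse only where 1.187 + 0.206 ln m = 0.812, that is, below about 0.16 mg.

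**Step 3: primary test, share of simulated trials with p < 0.05.**

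| Zeros, IQOS-M v IQOS-T | True CPE | 1 mg | 0.5 mg | 0.25 mg |
|---|---|---|---|---|
| 0.3% v 6% | 0.8 v 0.8 | 8% | 5% | 10% |
| 1% v 11% | 0.8 v 0.8 | 16% | 6% | 20% |
| 2% v 16% | 0.8 v 0.8 | 24% | 4% | 28% |
| 3% v 3% | 0.8 v 0.8 | about 5% | about 5% | about 5% |
| 2% v 16% | 1.0 v 0.8 | 26% | 86% | 99% |
| 3% v 3% | 1.0 v 0.8 | 82% | 89% | 91% |

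In the 1% v 11% row, false rejections at 1 mg nearly all put IQOS-T higher, and those at 0.25 mg nearly all put IQOS-M higher. A separate simulation of about that imbalance gave 15%, 5% and 14%. Grids of five to eight prices gave 13–17%, 4–6% and 13–20%.

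**Step 4: group-level slope.** Averaging raw demand and then taking the log gave mean slope differences of −0.03 to 0.00 when the truth was 0, and +0.17 to +0.20 when it was +0.20, at every mg value. No arm mean was zero in any run. Taking logs first with 0.1 (2% v 16%, truth 0) gave −0.09, −0.01 and +0.08 at 1, 0.5 and 0.25 mg.

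**Step 5: its standard error.** If the linear-combination comparison means ordinary least squares on the averaged points, it rejected equal CPE in 51–65% of runs, including 60–65% with balanced zeros. A separate simulation gave 63–67%. The residuals around a line through arm means do not carry the variation between participants. A leave-one-participant-out jackknife rejected in 5–7%, with interval coverage of 93–95%.

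**Step 6: would the imbalance be seen?** Zeros of 2% v 16% required about a 3.3-fold difference in IQOS demand, with zeros at the lowest price near 10% v 54%. The planned comparison of demand at that price then rejected in 99% of runs.

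**The case against.** The strongest reply is that the plan already contains what is needed. The comparison of observed IQOS demand at the lowest cigarette price uses no constant and would expose a large imbalance. That stands. However, it reveals the imbalance without correcting the elasticity comparison.

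The wording is also clearer than a strict reader might allow. The sentence alters the zeros, mg is the natural scale, and calling 0.1 an integer is a slip. Averaging demand and then fitting a model for log demand most naturally means averaging first. A reader might infer that the plan averages logs, or leaves the order open in a damaging way. The text does not support that; it merely leaves the order unstated.

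A reader might also infer that the choice of mg per stick reverses the order of the two buyers in Step 2. It does not at any value from 0.25 to 1 mg. Ranks soften the dependence, and the case rests on the simulated trials, not on that pair.

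The mg conversion is referred to an appendix that is not in the supplied text, so it cannot be called missing from the plan. At 0.5 mg per stick the test is close to nominal.

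Finally, the standard-error problem arises with balanced zeros too, so it is not evidence about the 0.1. It belongs here because the group-level slope is the available check, and the least-squares reading of the comparison is itself an assumption.

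**Conclusion.** The point holds in a limited form. The primary H1D slopes depend on the 0.1 for participants with both zero and positive IQOS purchases, and no planned analysis varies it. Under the assumed imbalances, false rejection ranged from nominal to 28%, and power for a true difference of 0.20 ranged from 26% to 99%. With balanced or rare zeros the effect is negligible.

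Size and direction depend on the mg per stick, the prices above $0.12 and the zero shares, none of which is in the supplied text. A reader might conclude that the H1D test is invalid, or biased in favor of IQOS-menthol. The documents support neither: the direction reverses between 1 and 0.25 mg per stick, and an imbalance in zeros is plausible but not shown.

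The firmer part concerns the alternative analysis. If its slopes are compared with standard errors from the averaged points, it cannot serve as a check, because it rejects equal elasticities about 50% to 65% of the time.

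**What to change.** Keep the individual-slope Mann-Whitney test with 0.1 as primary.

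- In the group-level analysis, state that raw demand, zeros included and no constant added, is averaged within arm at each price before the log.
- Base the standard error of the slope difference on a leave-one-participant-out jackknife or a participant bootstrap.
- Report that difference beside the primary result as the constant-free check, with the share of zero IQOS purchases by arm and price and the planned comparison at the lowest price.
- If the primary test is repeated with other constants, keep them close to 0.1 and below the mg of one stick, for example 0.05 and 0.2. On the six-price grid, each moves a single lowest-price zero by 0.693 × 0.206 = 0.14. Avoid 0.01 and 1: at equal CPE with unbalanced zeros they rejected in 26–56% and 54–95% of runs, depending on the scenario. Treat such repeats as disclosure, not as a condition for supporting H1D.
- As a tidy-up, replace the word integer and say that 0.1 is in mg and applies to zeros only, if that is what is meant.

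The cost is a few sentences of SAP text and short analyses of data already collected by the task. The group-level check has less power than the primary test (about 53% against 86% at 0.5 mg, true difference 0.20, zeros 2% v 16%), so its failure to reach significance would not refute H1D. The H1D statement may become more cautious. Since the section is written in the past tense, analyses added after the data were seen should be labelled as such.

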### $log(Demand) = \beta_0 + \beta_1 log(OB Menthol Cigarette Price) + e,$

where  $\beta_0$  represented the cross-price intensity of demand,  $\beta_1$  represented the CPE of the fixedprice alternative as a function of OB menthol cigarette price (main outcome), and *e* was the error term. Mann-Whitney U tests compared the individual-level CPE estimates for IQOS across participants with access to both flavors of HeatSticks (IQOS-M group) to participants with access to only Regular/Tobacco HeatSticks (IQOS-T group) at the final clinical laboratory session (IQOS; Fri, week 2; session 4, study day 12). As an alternative strategy for calculating CPE estimates, demand for each fixed-price alternative was averaged within-group at each price trial in the ETM then a single regression for each group was fit to Equation 1. The resulting  $\beta_1$ coefficient estimates were compared across experimental groups using a linear combination of parameters approach.

To ensure data quality and that participants were responding to the price cues within the task, demand for OB menthol cigarettes in the ETM was modeled using an exponentiated demand equation (GraphPad Prism 9; Hursh & Silberberg, 2008),

$$Q = Q_0 + 10 * k (e^{(-\alpha(C * Q_0))}) - 1),$$

where *C* represented the cost of the OB menthol cigarettes, *Q* represented cigarette consumption at price *C*, *Q*0 represented OB menthol cigarette demand intensity (i.e., cigarette consumption at the lowest price trial), *k* represented the range of cigarette demand across price trials in log units, and  $\alpha$  was the free parameter that represented the rate of change in demand elasticity. *k* was set equal to 4.89 for all participants (Hursh & Roma, 2013; Hursh & Silberberg, 2008; Quisenberry, Koffarnus et al., 2016). Group-level averages for  $\alpha$  and R^2 were the outcomes of interest;  $\alpha$  was expressed in terms of log( $\alpha$ ) because  $\alpha$  values tend to be very small. OB menthol cigarette demand was also assessed for each participant using criteria (i.e., trend, bounce, reversal from zero) for identifying nonsystematic demand in purchase tasks (Stein, Koffarnus et al., 2015).

Exploratory analyses compared the observed *cross-price intensity* of IQOS (i.e., demand for IQOS at the lowest price of OB menthol cigarettes [\$0.12/cigarette]) across the IQOS-M and IQOS-T groups using Mann-Whitney U tests. CPE estimates for all other alternative products were compared across experimental groups using Mann-Whitney U tests (individual-level analyses) and a linear combination of parameters (group-level analyses). Wilcoxon Signed Rank tests compared ETM outcomes (within-group) across sessions 2 (OB, Fri) and 4 (IQOS, Fri) as well as across sessions 3 (IQOS, Mon) and 4 (IQOS, Fri) to gauge if exposure to IQOS in the clinical laboratory or at home influenced purchasing decisions in the ETM.

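### The group-level cross-price-elasticity comparison takes its error from averaged points rather than from participants, so its type I error is uncontrolled and may be too high or too low

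*Combined protocol and SAP*

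**What the plan says.** Hypothesis H1D, on the CPE of IQOS with respect to own-brand menthol cigarettes, is one of three that "constitute primary outcomes. All other hypothesis represent secondary outcomes" (section 1, Objectives). Section 6 (Study Procedures, Aim 1) says of the ETM task: "The primary outcome of interest is the cross-price elasticity of demand for IQOS as a function of OB price".

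Section 9 (Aim 1 Analyses, Experimental Tobacco Marketplace) gives two routes to the between-arm comparison.

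- **Participant level.** A log-log regression gives one slope per participant, and "Mann-Whitney U tests compared the individual-level CPE estimates for IQOS across participants" in the two arms at the final laboratory session.
- **Group level.** The second route opens with the words "As an alternative strategy for calculating CPE estimates". Its first step is that "demand for each fixed-price alternative was averaged within-group at each price trial in the ETM then a single regression for each group" is fitted. Its second step is the test: the two slope "coefficient estimates were compared across experimental groups using a linear combination of parameters approach".

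The exploratory paragraph applies both routes to every other alternative product, the second described as "a linear combination of parameters (group-level analyses". No clustered, bootstrap, mixed-model or other participant-level variance is named for the group-level route. The plan also does not say whether averaging comes before or after the log transformation.

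**The concern.** Averaging reduces about 25 participants per arm to one point per price. The only scatter left in the regression is that of the arm means around the fitted line. Two faults follow if the standard error comes from that fit.

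1. Participants differ in how steeply their IQOS demand responds to cigarette price. This variation adds to the uncertainty of each arm's slope, but a participant with a steep straight line tilts the mean line and adds little or no scatter around it. The standard error is then too small.
2. Any departure from a straight line that both arms share enters the residuals but largely cancels in the slope difference. Curvature is one source. Order effects are another, because section 6 says that "within a session each participant will face the same order of price-trials". The standard error is then too large.

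The faults pull in opposite directions, and nothing in the documents shows which dominates. A spurious flavour difference could be reported beside the primary H1D result or for another product, or a real one could be missed.

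**Working it through.** The plan states no standard error, power or error rate for this comparison, so there is no figure to reproduce.

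**Inputs from the document:** 25 participants per arm (section 3); lowest price $0.12 per cigarette and a log-log model (section 9). **Assumptions:** prices doubling from $0.12, with 5, 6 or 8 of them; log10 units; between-participant intercept SD 0.3, slope SD s_b of 0.2 or 0.3, and residual SD s_e of 0.2; a pooled-variance t-test of the slope difference on 2P − 4 degrees of freedom for P prices.

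**Algebra (logs averaged, straight lines).** With n per arm and Sxx the sum of squares of centred log price:

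- true variance of the slope difference = 2(s_b²/n + s_e²/(n·Sxx));
- variance that least squares on the arm means estimates = 2·s_e²/(n·Sxx), plus any lack of fit.

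The term in s_b² is lost. For 8 prices Sxx = 3.806. With s_b = 0.3 and s_e = 0.2:

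- true SE = √[2(0.09/25 + 0.04/(25 × 3.806))] = √[2(0.00360 + 0.00042)] = 0.090;
- SE from the arm means = √(2 × 0.00042) = 0.029, too small by a factor of 3.09.

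The critical value 2.179 (12 df) therefore acts like 2.179/3.09 = 0.705, which a t variable on 12 df exceeds in absolute value 49% of the time. The same steps give 21% at 5 prices and 31% at 6.

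**Simulation.** Rejection rates with no true difference, 10,000 trials per setting. Curvature is the coefficient on squared centred log10 price, common to both arms.

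| Setting | 5 prices | 6 prices | 8 prices |
|---|---|---|---|
| *Demand averaged, then logged* | | | |
| Identical slopes | 5% | 5% | 5% |
| Slope SD 0.1 | 7% | 8% | 13% |
| Slope SD 0.2 | 11% | 17% | 28% |
| Slope SD 0.3 | 17% | 23% | 33% |
| Slope SD 0.3, residual SD 0.6 | 6% | 7% | 10% |
| Slope SD 0.2, curvature +0.15 | 6% | 6% | 4% |
| Slope SD 0.2, curvature −0.15 | 10% | 13% | 17% |
| Slope SD 0.2, curvature +0.3 | 1.5% | 0.5% | 0.1% |
| Slope SD 0.3, curvature −0.15 | 18% | 26% | 39% |
| Slope SD 0.2, shared order effect SD 0.1 | 1% | 2% | 5% |
| Slope SD 0.3, shared order effect SD 0.1 | 3% | 5% | 12% |
| *Logs averaged* | | | |
| Slope SD 0.2 | 13% | 19% | 34% |
| Slope SD 0.3 | 20% | 31% | 49% |

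The last row agrees with the algebra (21/31/49%). A separate simulation with residual SD 0.3 and 5 to 10 prices showed the same pattern. It gave about 5% with identical slopes and exact linearity, up to 65% with a slope SD of 0.5 and 10 prices, and close to zero with strong shared curvature. In that simulation the Mann-Whitney test on individual slopes rejected in 4.3–5.2% of trials in every setting.

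**Repairs.** These were compared over 2,000 trials per scenario at 5 and 8 prices, with assumed strata of 16/14/10/10. Scenarios were straight lines, curvature, a shared order effect, and a switch-price pattern in which 30% never buy.

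| Method | Straight, curved and order-effect scenarios | Switch-price scenario |
|---|---|---|
| Jackknife over participants (t, 48 df) | 3.7–5.2% | 6.2–8.1% |
| Percentile bootstrap over participants | 6.2–7.4% | 9.0–10.3% |

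Over all scenarios, the planned test rejected in 0.5–44.2% of trials, permutation within strata in 4.5–5.4%, and participant-level Mann-Whitney in 3.6–4.8%.

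**The case against.** The strongest reply is about scope. The averaged fit is labelled an alternative, the other-product comparisons are exploratory, and the Mann-Whitney test of H1D is sound. The hierarchy can also be inferred: the Mann-Whitney sentence names the endpoint session, and the other main outcomes are compared by the same kind of test. All of this stands, and it is why the point does not threaten the primary analysis. Even so, the main-outcome label is attached to the slope that both routes estimate, and no sentence says which result decides H1D.

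A second reply is that the plan names no variance estimator, so the t-test on arm means is a reading of the text and not a quotation from it. That is fair, and the conclusion is conditional on it. But a single regression per arm on averaged demand has no participant-level information left in it. If a participant-level method was used, the plan needs to say so.

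A third reply is that the rates rest on assumed prices, SDs, curvature and order effects, and that some settings are near nominal. This is also true: a large residual SD or a small slope SD brings the rate close to 5%. It limits what can be said about size, but does not restore a known error rate.

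**Conclusion.** The concern holds. Followed as written, the group-level comparison uses a standard error that leaves out most or all of the between-participant slope variance and takes in misfit shared by the arms. It is assured of its nominal level only if participants' slopes do not vary and the log-log line fits exactly. In the illustrative settings tabulated above, a nominal 5% test rejected in anything from 0.1% to 49% of null trials. These are not bounds, and the direction cannot be told from the documents. The conclusion is conditional on no unstated participant-level variance method having been used. It affects the alternative analysis of H1D and the exploratory group-level comparisons of the other products. It does not affect the participant-level test of H1D or the sample size. It should be fixed.

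**What to change.** **Preferred:** report the averaged curves and their slopes as descriptive only, without p-values, for IQOS and all other ETM products.

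**Otherwise:** keep the averaged-curve slopes, and obtain the between-arm p-value by permuting participants' arm labels within the gender-by-race strata of section 2, repeating the averaging and fitting each time. If an interval is wanted, resample participants and call it approximate. At 25 per arm the percentile bootstrap over-rejects, as does the jackknife when many zeros occur, so an interval may disagree with the permutation p-value.

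**In either case:** add one sentence saying that the participant-level Mann-Whitney result decides H1D, and state whether demand is averaged before or after taking logs. The analysis text is in the past tense; if the analysis has already been run, label the re-analysis as post hoc.

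**Cost:** a little wording, or a few lines of code; no new data. Intervals may widen or narrow. At slope SD 0.3, mean width from the planned method to the jackknife goes from 0.24 to 0.48 (8 prices, straight lines), 0.64 to 0.48 (8 prices, curvature +0.3) and 0.78 to 0.55 (5 prices, shared order effect SD 0.1).
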